**TABLE 1: SCHEDULE OF STUDY PROCEDURES**

Study Phase	Screening (Phone)	Baseline (PCTRc)	Run-In (Home)	Assign Goal (Phone)	Intervention (Home)	Interim Visits (Phone)	Follow-up (PCTRc)
Visit Number		1		2		3, 4	5
Study Days			2-weeks	Within 1 week of run-in	12-week intervention	Weeks 2 and 6 of Intervention	Up to 2 weeks after Intervention
Verbal Consent/Assent	X						
Review Inclusion/Exclusion Criteria	X	X		X			
Written Documentation of Consent/Assent		X					
Demographics/Medical History		X					
Physical Examination		X					X
Vital Signs: BP, HR, RR		X					X
Anthropometry		X					X
Urine Pregnancy Test		X					
Prior/Concomitant Medications		X					X
Clinical Laboratory Evaluation		X					X
Individual interview, surveys		X					X
Dietary recall					X		
Randomization				X			
Provide/Collect Fitbit		X					X
Fitbit compliance, goal review			X	X		X	
Assess baseline physical activity			X	X			
Adverse Event Assessment				X		X	X
Daily Fitbit use			X		X		

**FIGURE 1: STUDY DIAGRAM**

## 1 BACKGROUND INFORMATION AND RATIONALE

### 1.1 Introduction

Obese adolescents and young adults with type 2 diabetes are significantly less active than non-diabetic peers, despite the many cardiovascular and diabetes-related benefits of physical activity. Mobile health (mHealth) strategies offer benefits over in-person physical activity interventions including convenience, but convenience alone is unlikely to significantly alter behavior. The BEAM Trial (Behavioral Economics for Activity Motivation in Adolescents and Young Adults with Prediabetes and Type 2 Diabetes) seeks to be the first to use behavioral economic principals, combined with traditional health behavior change theory, in an mHealth intervention to effectively motivate obese adolescents and young adults with prediabetes and type 2 diabetes to increase moderate to vigorous physical activity (MVPA). This work is supported by a funded NIH K23 Career Development Award. The trial will use Way to Health (W2H), a web-based platform that allows two-way text messaging, delivery of behavioral economic-informed financial incentives, and integration with the physical activity tracker Fitbit.

### 1.2 Name and Description of Intervention

This trial will evaluate four intervention components (“factors”), each with two levels: once- or twice-daily behavior change theory-informed text messages, loss- versus gain-framed financial incentives, weekly versus daily step count goals, and ramped versus fixed stepcount goals.

### 1.3 Relevant Literature and Data

**Youth-onset T2D is rising in incidence and associated with severe comorbidities, but effective methods of delaying or preventing disease progression are lacking.** The incidence of youth-onset T2D is rising, with the greatest rate of increase among racial and ethnic minorities.(Mayer-Davis, Lawrence et al. 2017) Youth-onset, as compared to adult-onset T2D is especially worrisome due to faster decline in pancreatic beta-cell function,(Nadeau, Anderson et al. 2016) as well as high rates of diabetes-related complications soon after diagnosis, including elevated blood pressure (14%), microalbuminuria (13%), low HDL cholesterol levels (80%), and high triglycerides (10%).(Copeland, Zeitler et al. 2011) Individuals with youth-onset T2D also face a striking 15-year reduction in life expectancy.(Rhodes, Prosser et al. 2012) Unfortunately, effective medications to preserve beta-cell function in youth are lacking,(Consortium 2018) leaving only lifestyle interventions to reduce obesity-related risks.

**Physical inactivity is an important modifiable risk factor for individuals with T2D and prediabetes.** Physical activity in youth is associated with decreased fasting insulin, increased insulin sensitivity(Ho, Garnett et al. 2013, Lee, Deldin et al. 2013, Fedewa, Gist et al. 2014) and improved body composition,(Lee, Deldin et al. 2013) and youth with T2D are recommended to engage in at least 60 minutes of MVPA daily, the same as for healthy youth.(Copeland, Silverstein et al. 2013, Colberg, Sigal et al. 2016) However, youth with T2D are significantly less active than obese youth without T2D, ranging from 8 minutes per day of MVPA in 15-18 year-old girls to 35 minutes per day in 10-14 year-old boys.(Kriska,

Delahanty et al. 2013) Overweight youth in Philadelphia are similarly failing to meet activity recommendations: only 31% reported being physically active for  $\geq 5$  hours per week, while 30% reported being active for  $\leq 2$  hours per week.(Dearick, Klusaritz et al. 2019)

Example activities that constitute MVPA in youth include walking  $> 4.0$  miles/hour, team sports, jogging, biking, and housework including sweeping and vacuuming.(Butte, Watson et al. 2018) Longer average time spent in MVPA daily is negatively associated with body mass index Z-score in youth. Increased physical activity can reverse impaired glucose tolerance, impaired fasting glucose, and elevated hemoglobin A1c in youth(Weiss, Taksali et al. 2005, Savoye, Caprio et al. 2014, Love-Osborne, Sheeder et al. 2017) and adults(Knowler, Barrett-Connor et al. 2002) with prediabetes, although evidence for improvement in glycemic control is mixed for youth with T2D,(Group, Zeitler et al. 2012, Herbst, Kapellen et al. 2015) likely reflecting differences in intervention design. In addition to a potential impact on glycemic control, greater PA has been associated with improved perception of physical abilities among youth with T2D,(O'Neill, Liese et al. 2012) as well as improvement in depression,(Brown, Pearson et al. 2013, McGavock, Dart et al. 2015) psychological well-being, executive functioning, and school performance(Pivovarov, Taplin et al. 2015) among children and adolescents without diabetes. Even time spent in low-intensity physical activity has been associated with improved diastolic blood pressure and higher HDL in adolescents(Carson, Ridgers et al. 2013) as well as lower prevalence of hyperglycemia(Manders, Van Dijk et al. 2010) and greater insulin sensitivity(Newsom, Everett et al. 2013) in adults with T2D. Due to the potential benefits of increased physical activity for AYA with prediabetes and T2D, methods to successfully promote engagement in PA interventions are needed.

**Mobile health (mHealth) interventions are a promising way to promote health behavior change in youth.** In-person lifestyle interventions(Elvsaa, Giske et al. 2017) face challenges with scalability due to the need for dedicated space and multidisciplinary staff, and in-person interventions have high attrition rates, particularly among economically disadvantaged and minority youth.(Zeller, Kirk et al. 2004) mHealth strategies have been used successfully for a wide variety of health behavior change interventions in youth(Fedele, Cushing et al. 2017) and allow interventions to be more scalable, especially given the near-ubiquity of smartphone use among adolescents.(Pew Research Center)

**The effectiveness of mHealth-based interventions can be improved through the use of behavior change theories as well as strategies to promote user engagement.(Vandelanotte, Muller et al. 2016)** Use of health behavior change theories can allow for systematic identification of targets for behavior change interventions.(Glanz, Rimer et al. 2015) The Theory of Planned Behavior (TPB),(Ajzen 1991) a commonly used model for adolescent and adult health behavior change interventions,(Muzaffar, Chapman-Novakofski et al. 2014) suggests that *intention* to engage in a behavior is the proximal determinant of that behavior. Intention, in turn, is predicted by the 3 main constructs of the TPB: attitude (belief about consequences of behavior combined with evaluation of consequence), subjective norm (belief about what others want one to do and motivation to comply), and perceived behavioral control (belief about amount of control one has to successfully perform the behavior).

---

Although the TPB posits that behavior follows intention, the field of behavioral economics (BE) emphasizes that humans do not always act in their best interest and applies psychological insights to explain behaviors that are in apparent opposition to health behavior goals. BE-informed interventions have been used in numerous studies of adults to promote health behavior change.(Volpp, John et al. 2008, Patel, Asch et al. 2016, Patel, Benjamin et al. 2017, Patel, Volpp et al. 2018, Glanz, Shaw et al. 2019) One BE insight is that framing, or the presentation of the same information in ways that highlight different informational cues, can significantly impact decision-making.(Thaler 1999, Dhami 2016) As losses tend to be felt more acutely than gains (*loss aversion*),(Kahneman and Tversky 1979, Patel, Asch et al. 2016, Wong, Miller et al. 2017) presenting information in a “loss-framed” manner tends to be a convincing strategy. In addition, the concept of *delay discounting* describes the tendency to prefer smaller rewards sooner over larger rewards later.(Laibson 1997) Higher rates of delay discounting have been associated with worse glycemic control and lower physical activity among adults with prediabetes and type 2 diabetes.(Epstein, Paluch et al. 2020) Although use of traditional behavior change theories is common among mHealth-based interventions, application of BE principals to the design of behavior change interventions has been understudied.

**Motivation to perform health behaviors such as physical activity can be intrinsic or extrinsic, which may have implications for success and persistence of behavior change.(Ryan and Deci 2000)** According to the Self-Determination Theory, intrinsic and extrinsic motivation (divided into external, introjected, identified, and integrated regulation) fall on opposite ends of a continuum.(Ryan and Deci 2000) *Intrinsic regulation* represents a desire to engage in an activity for its own sake, while *extrinsic regulation* represents engagement in activity only to achieve outcomes or to satisfy a requirement (such as meeting a step count goal to obtain a financial incentive). *Introjected regulation* refers to motivation to perform an activity in order to avoid negative feelings; *identified regulation* represents a willingness to perform an activity that is not enjoyable in order to remain consistent with personal values; and *integrated regulation* falls between identified regulation and intrinsic regulation and represents performance of an activity because it is consistent with one’s values and needs. *Amotivation* refers to a lack of intention to engage in an activity. Previous studies have found that more autonomous/less extrinsic motivation is associated with greater physical activity in children and adolescents.(Owen, Smith et al. 2014, Navarro, Escobar et al. 2020) Measuring and understanding whether the degree of intrinsic or autonomous motivation changes when extrinsic rewards are offered will add depth to the findings of our proposed intervention.

#### **1.4 Compliance Statement**

This study will be conducted in full accordance all applicable Children’s Hospital of Pittsburgh and University of Pittsburgh Research Policies and Procedures and all applicable Federal and state laws and regulations including 45 CFR 46. All episodes of noncompliance will be documented.

The investigators will perform the study in accordance with this protocol, will obtain consent and assent, and will report unanticipated problems involving risks to subjects or others in accordance with institutional Policies and Procedures and all federal requirements.

Collection, recording, and reporting of data will be accurate and will ensure the privacy, health, and welfare of research subjects during and after the study.

## **2 STUDY OBJECTIVES**

The purpose of the study is to determine the efficacy of multiple components of an mHealth intervention aimed at promoting increased physical activity in adolescents with prediabetes or T2D.

### **2.1 Primary Objective**

The primary objective is to determine the main and interactive effects of four experimental factors (*once- versus twice-daily behavior change theory-informed text messages, loss- versus gain-framed financial incentives, daily versus weekly step count goals, and ramped versus fixed step count goals*) on time spent in moderate to vigorous physical activity.

### **2.2 Secondary Objectives**

The secondary objectives are to:

- Determine the main and interactive effects of the four intervention components on:
  - Daily step count
  - body mass index Z-score
  - hemoglobin A1c
  - fasting insulin
  - fasting plasma glucose
  - fasting triglycerides, LDL, and HDL
  - AST, ALT
- Explore participant-reported intervention acceptability, including constructs of burden, perceived effectiveness, and impact on self-efficacy
- Assess baseline and intervention-related changes in intrinsic versus extrinsic motivation to pursue physical activity
- Assess the association between baseline delay discounting tendency and baseline and change in MVPA and step count
- Assess the correlation between Fitbit-measured physical activity and smartphone-measured physical activity

### 3 INVESTIGATIONAL PLAN

#### 3.1 General Schema of Study Design

This factorial trial will include screening by phone, completion of two in-person and two phone study visits, completion of dietary recalls by phone at home, and daily wearing of Fitbit physical activity tracker during waking hours for a 14-day run-in period and 12-week intervention.

##### 3.1.1 Screening Phase

Potential subjects will be identified through weekly review of Pediatric Endocrinology and Diabetes clinic schedules. In addition, a list of potentially eligible patients will be generated via review of a list of patients with diagnosis of prediabetes or type 2 diabetes provided by Pitt+ME. Medical records of potential subjects will be screened by the study team using the protocol inclusion and exclusion criteria. The CAYAH RESEARCH INTEREST FORM will also be used for recruitment purposes. This is a REDCap form with a survey link that will contain questions for adolescents to answer self-screen questions which are non-sensitive. Center for Adolescent and Young Adult Health (CAYAH) clinical staff will manage and distribute this survey. CAYAH clinical research staff will advertise the study to the teen. If the teen (age 13 or older) indicates interest in the study by viewing the study advertisement within the CAYAH RESEARCH INTEREST FORM, they will provide their contact information to the CAYAH clinical research staff who will then share it with the study team. Those who appear to meet the criteria will be approached by a member of the study team by phone and asked if they would like to hear about the study. Subjects and/or their parent/guardian will provide demographic, social, and medical information about themselves, their child, or family (as applicable) to confirm eligibility. Subjects will complete an overnight fast at home prior to the baseline study visit.

##### 3.1.2 Baseline Study Visit (Visit 1)

After a 12-hour overnight fast at home, participants will attend Visit 1 at PCTR to obtain baseline physical and biochemical data, as well as to complete individual interviews and surveys. At that visit, participants will be given a Fitbit to use during the study and instructed on its use. Participants will download the Fitbit app on their smartphone for use during the study. Participants will also work with a study team member to form an individualized implementation intention statement, which will include specific details about what, when, and where the subject will participate in a physical activity of choice, as well as contingency plans to help promote completion of planned activities.

##### 3.1.3 Run-In

To determine baseline physical activity (MVPA), participants will be asked to wear the provided Fitbit for 14 consecutive days during waking hours and to sync the Fitbit daily with the app on their smartphone. They will also receive reminder text messages twice daily. Participants with mean daily MVPA >30 minutes or with < 4 days of Fitbit wear during the second week of run-in will be withdrawn from the study and will not continue on with the intervention. All participants will be called by phone (Visit 2) to review whether they will proceed to the intervention or not. Withdrawn participants will be asked to return the Fitbit using a prepaid envelop.

### **3.1.4 Intervention**

The 12-week intervention will consist of text messages sent to the participant and financial incentives that are dependent on compliance with step count goals. Eligible participants will be randomized and individualized step count goals for the intervention will be reviewed. The participant will be instructed that the intervention will begin on the following Monday and will last for 12 weeks.

During week 2 of the intervention, study staff will call the participant by phone to review adverse events or other safety concerns (Visit 3). During week 6 of the intervention, study staff will call the participant by phone (Visit 4) to obtain feedback from the participant on the intervention and to troubleshoot any issues with the Fitbit.

Dietary recalls (3) will be conducted by phone during the first two weeks of the 12-week intervention.

### **3.1.5 Follow Up Study Visit (Visit 5)**

Within 2 weeks of completing the 12-week intervention, participants will be requested to return to PCTRCC for Visit 5 to obtain follow-up physical and biochemical data, as well as exit interview. Participants will be asked to fast for a minimum of 12 hours before the visit, and will be asked to return the Fitbit at study visit 5.

## **3.2 Allocation to Treatment Groups and Blinding**

### **3.3 Allocation to Treatment Groups**

Participants will be randomized via Way to Health to 1 of 16 experimental conditions (4 factors, with 2 levels each; e.g., twice-daily text messages + loss-framed incentive + weekly goals + ramped goals = one experimental condition).

## **3.4 Study Duration, Enrollment and Number of Sites**

### **3.4.1 Duration of Subject Study Participation**

Each in-person study visit is expected to take approximately 1-1.5 hours. Screening, phone study visits, and dietary recalls are expected to take approximately 30 minutes each. The entire study duration per subject is planned to last a maximum of 17-weeks (2-week run-in, up to 1 week between run-in and intervention, 12-week intervention, ending with study visit up to 2 weeks after completion of intervention). However, the time window between completion of the intervention and Visit 5 could be adjusted due to public health recommendations, and/or local, state, federal, and/or institutional guidelines.

### **3.4.2 Total Number of Study Sites/Total Number of Subjects Projected**

This study will be conducted at the Children's Hospital of Pittsburgh. A maximum of 75 subjects will be included.

## **3.5 Study Population**

We will not restrict enrollment based on gender or age within the eligible age group.

We plan to enroll only English-speaking patients.

### **3.5.1 Inclusion Criteria**

- 1) Males or females age 13 to 22 years.
- 2) Overweight or obese (BMI  $\geq 85^{\text{th}}$  percentile for age/sex, or  $\geq 25 \text{ kg/m}^2$  for participants  $\geq 18$  years)
- 3) Diagnosis with a condition associated with insulin resistance, including prediabetes or type 2 diabetes.
- 4) Consent (subjects 18 and older), Parental/guardian permission (subjects 13-17), assent (subjects 13-17)
- 5) Willingness to wear Fitbit during waking hours daily for duration of run-in and intervention.
- 6) Possession of a smartphone with data plan.

### **3.5.2 Exclusion Criteria**

- 1) Potential subject unable to speak or read in English
- 2) Severe cognitive impairment
- 3) Permanent or temporary physical disability that impairs ambulation or precludes engagement in MVPA
- 4) Current pregnancy
- 5) Previously-diagnosed or current restrictive or purging eating disorder
- 6) MVPA  $> 30$  minutes per day or Fitbit wear  $< 4$  days during second week of 2-week run-in period

Subjects that do not meet all of the enrollment criteria may not be enrolled. Any violations of these criteria must be reported in accordance with IRB Policies and Procedures.

## **4 STUDY PROCEDURES**

### **4.1 Phone screening**

- Medical Record Review
- Brief study overview: 5 minutes
  - Consent/HIPAA Authorization: 5-10 minutes/as long as needed for full comprehension of study involvement
  - Screening questionnaire: 15 minutes

---

- Overview of 12-hour overnight fast and upcoming screening visit: 5 minutes

## 4.2 Visit 1

- Vital signs (heart rate, blood pressure): 5 minutes
- Urine pregnancy test (all females): 3 minutes
- Height, weight, waist and hip circumference: 5 minutes
- Focused physical exam, including pubertal status: 5 minutes
- Fasting blood draw: 10 minutes
- Baseline questionnaires: 30 minutes
- Coach participant to form implementation intention statement about physical activity: 10 minutes
- Provide Fitbit, help participant download app, and instruct on use: 5 minutes

## 4.3 Run-In and Randomization

### 4.3.1 2-Week Run-In

- Participant wears Fitbit daily during waking hours and syncs daily with smartphone
- Daily text message reminder sent to participant
- On day 15, study team will evaluate MVPA during days 8-14
  - Exclude from intervention if mean > 30 minutes/day or if < 4 days with evaluable Fitbit data
- Calculate mean daily step count during days 8-14, to provide to participant for reference

### 4.3.2 Visit 2 (Phone)

- Randomize to 1 of 16 experimental conditions

Experimental Condition	Text	Ramped goal	Incentive Framing	Goal time period
1	+	+	+	+
2	+	+	+	-
3	+	+	-	+
4	+	+	-	-
5	-	+	+	+
6	-	+	+	-
7	-	+	-	+
8	-	+	-	-
9	+	-	+	+
10	+	-	+	-
11	+	-	-	+
12	+	-	-	-
13	-	-	+	+
14	-	-	+	-
15	-	-	-	+
16	-	-	-	-

**Figure 2.**  $2^4 = 16$  experimental conditions

- Call participant to:
  - Review assigned step count goal
  - Explain financial incentive structure
  - Troubleshoot concerns related to Fitbit or text messages
  - If not eligible based on run-in: inform participant of study completion and request return of Fitbit via prepaid envelope

#### 4.4 12-Week Intervention

##### 4.4.1 Dietary recalls (phone)

- 2 weekday, 1 weekend recall during weeks 1-2 of intervention: 3 x 30 minutes each

##### 4.4.2 Visit 3 (phone), Intervention Week 2

- Assess possible adverse events

##### 4.4.3 Visit 4 (phone), Intervention Week 6

- Assess possible adverse events

- Medical Record Review
- Troubleshoot any concerns related to Fitbit or text messages

## **4.5 Study Completion**

### **4.5.1 Visit 5, within 2 weeks of Intervention completion**

- Medical Record Review
- Assess possible adverse events: 5 minutes
- Current medications: 3 minutes
- Vital signs (heart rate, blood pressure): 5 minutes
- Height, weight, waist and hip circumference: 10 minutes
- Fasting blood draw: 10 minutes
- Individual exit interview: 30 minutes
- Collect Fitbit

## **4.6 Subject Completion/Withdrawal**

Subjects may withdraw from the study at any time without prejudice to their care. They may also be discontinued from the study at the discretion of the Investigator for lack of adherence to study treatment or visit schedules, AEs, or due to adherence to study treatment or visit schedules. The Investigator may also withdraw subjects who violate the study plan, or to protect the subject for reasons of safety or for administrative reasons. It will be documented whether or not each subject completes the clinical study. If the Investigator becomes aware of any serious, related adverse events after the subject completes or withdraws from the study, they will be recorded in the source documents and on the case report form (CRF) on REDCap.

Fitbit, questionnaire, interview, and clinical data obtained prior to subject withdrawal will be retained.

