### **4.6.1 Early Termination Study Visit**

Subjects who withdraw from the study will have all procedures enumerated for Visit 5 as the early termination visit if at least 4 weeks have elapsed since the start of the 12-week intervention.

---

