#### 6.5.4 Missing Data

Step count and MVPA data may be missing for any day if the Fitbit is not used or not synced. To prevent potential downward bias from very low minutes per day, we will ignore days in which fewer than 1000 steps are recorded, as this likely represents a failure to capture actual activity.(Rowe, Mahar et al. 2004, Patel, Benjamin et al. 2017) We will use multiple imputation for missing data or days with fewer than 1000 steps recorded, and results will be combined using standard rules.(Rubin 1987, Allison 2002) Predictors will include baseline daily minutes in MVPA, experimental condition, week in study after baseline (1-12), calendar month, and an indicator variable for weekday or weekend.(Patel, Benjamin et al. 2017) We will perform sensitivity analyses using all collected data without multiple imputation, including or excluding days with fewer than 1000 steps. Of note, mixed effects models allow for handling of incomplete and unbalanced data, making possible an intention-to-treat approach using the missing at random assumption. To minimize confounding for secondary outcomes, in a sensitivity analysis, subjects who start a new medication that may alter weight (including metformin, insulin, or glucagon-like peptide-1 receptor agonists) after visit 1 will have visit 5 weight, waist circumference, and laboratory measurements censored.

As an exploratory analysis, for days with missing Fitbit data, we will use participant-reported step count data recorded by their smartphones (sent via screenshot once weekly via text message to Way to Health).

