#### 8.1.2 Blinding

It will not be feasible to blind participants to the intervention components, and in fact would be undesirable to do so, as the intent of the behavior change intervention is to leverage behavioral economic insights to promote behavior change. Study staff will not be blinded, in order to ensure financial incentives are provided as intended and that assigned step count goals are communicated correctly to participants. During data analysis, each intervention component (factor) will be assigned a de-identified categorical value (A, B, C, D) with two de-identified levels (1, 2). Thus, the main and interactive effects of each intervention component can be evaluated in a blinded fashion.

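### Section 4.6 lets randomised participants be taken out of the study for poor adherence, which can make week-12 MVPA missing in a way that depends on activity and that the listed imputation predictors do not cover

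*Combined protocol and SAP*

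**What the plan says.** Section 4.6 (Subject Completion/Withdrawal) states: "They may also be discontinued from the study at the discretion of the Investigator for lack of adherence to study treatment or visit schedules". The removal is from the study, not only from the intervention, and no threshold is set. Later in the same sentence a further ground appears: "or due to adherence to study treatment or visit schedules". Read literally, both poor adherence and adherence are reasons for removal.

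On data, section 4.6 says: "Fitbit, questionnaire, interview, and clinical data obtained prior to subject withdrawal will be retained". Section 4.6.1 adds that subjects who withdraw "will have all procedures enumerated for Visit 5 as the early termination visit if at least 4 weeks have elapsed" since the intervention began. The Visit 5 list in section 4.5.1 includes "Collect Fitbit". No Fitbit collection after that point is described.

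Section 8.1.2 states: "Study staff will not be blinded, in order to ensure financial incentives are provided as intended".

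Section 6.1 makes mean daily MVPA in week 12 the primary endpoint, and section 6.5.1 analyses change to week 12 by ANOVA. Section 6.5.4 multiply imputes missing Fitbit days. The predictors it lists are baseline MVPA, experimental condition, study week, calendar month and weekday or weekend. It then remarks that mixed models handle incomplete data, "making possible an intention-to-treat approach using the missing at random assumption".

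**The concern.** Adherence and outcome are nearly the same thing in this trial. Under section 3.1.4 the incentives depend on meeting step goals, and under section 5.2 MVPA is counted from steps per minute on the same tracker. A participant judged non-adherent is therefore likely to be inactive, not wearing the device, or both. Ending that person's study participation before week 12 removes the primary endpoint for someone whose week-12 value would probably have been low.

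If this happens more often at one level of a factor, that level loses more of its least active members and its observed mean rises. The trial exists to decide which component settings to carry into an optimised intervention, so the error would favour the setting that engages people less well. The decision is discretionary and made in a setting where staff know the allocation, so nothing in the design prevents removal from differing by level.

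**Working it through.** **Step 1: the plan's own figure.** Inputs from section 6.6 and its Table 2: N = 64, difference 15 min, SD 20 min, two-sided alpha 0.05, stated power 0.84. A balanced two-level factor has 64/2 = 32 per level.

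- Standard error of a main effect: 2 × 20/√64 = 5 min.
- Effect-coded coefficient: 15/(2 × 20) = 0.375. Noncentrality: 0.375 × √64 = 3.0.
- Power from the noncentral t with 48 to 62 error degrees of freedom: 0.836 to 0.840. The normal approximation gives 0.851.

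The 0.84 reproduces. Recruitment also reproduces closely: 64/0.85 = 75.3, which rounds up to 76, against 75 planned. Neither figure is disputed.

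**Step 2: does week-12 MVPA survive removal?** Before 4 weeks, section 4.6.1 provides no early termination visit. From 4 weeks on, it provides the Visit 5 procedures, which give early anthropometry and laboratory values but take the tracker back. Either way, no week-12 Fitbit record is planned for a removed participant.

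**Step 3: possible size.** The documents give no rate of removal for non-adherence, so the removal rates and correlations below are assumptions. Suppose the lowest fraction q on earlier MVPA is removed at a level, and earlier MVPA correlates r with week-12 change. The mean of those remaining rises by r × 20 × φ(z_q)/(1 − q), where z_q is the normal quantile for q and φ the normal density.

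- q = 0.05: 20 × 0.1031/0.95 = 2.2 (times r)
- q = 0.15: 20 × 0.2332/0.85 = 5.5 (times r)
- q = 0.25: 20 × 0.3178/0.75 = 8.5 (times r)
- q = 0.30: 20 × 0.3477/0.70 = 9.9 (times r)

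The false difference between levels is r times the difference of these shifts. For 5% v 25% that is r × 6.3. With r = 0.4 it is 2.5, and with r = 0.8 it is 5.0.

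A simulation with 37 per level (75/2, rounded down), no true effect, 4,000 replicates and a complete-case comparison agrees:

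| Removal at the two levels | False difference, r = 0.4 to 0.8 (min/day) | Type I error |
|---|---|---|
| 15% v 15% | about 0 | about 0.05 |
| 5% v 25% | 2.5 to 5.0 | 0.07 to 0.19 |
| 0% v 30% | 3.9 to 7.9 | 0.11 to 0.37 |

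**Step 4: can the planned imputation repair this?** Imputing from the assigned condition alone returns the mean of those who stayed at that level, so it carries the same expected error. Baseline MVPA would recover part of it, to the extent that it predicts later activity. Calendar and weekday terms say nothing about who was removed. When the earlier observed MVPA was added as a predictor in the simulation, the false difference fell to within about 0.1 min/day of zero in every scenario in the table.

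**The case against.** A reader might infer that section 4.6 flatly contradicts intention-to-treat. The documents do not support that. Section 6.5.4 declares no intention-to-treat analysis set; it says only that mixed models make such an approach possible. Section 4.6 governs participation and drops nobody from the analysis. Earlier data are retained and missing days are imputed.

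A reader might also infer that outcome-dependent missingness is certain, or that unblinded staff will remove people unequally. The clause is permissive, and nothing shows how it would be used. Removal based on activity already recorded is compatible with missing at random in a mixed model that uses the weekly Fitbit data. Equal removal gives no bias under the null. The plan also seems to expect poor adherers to stay: section 6.5.3 analyses days with Fitbit data during the intervention, section 6.5.4 provides for unworn days, and under section 8.7.2 the incentive is tied to goal attainment.

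Nor is it right that nothing is collected after removal, because section 4.6.1 plausibly covers participants withdrawn by the Investigator. The second adherence clause looks like a drafting slip. And someone who has stopped wearing the tracker may give no week-12 data even if kept in follow-up.

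All of this limits the point, but does not remove it. The mixed models are additional to the ANOVA and take in the interactions that the ANOVA finds significant, so a distorted ANOVA can carry forward. The listed imputation predictors omit what removal would depend on, although the list may not be exhaustive. The sensitivity analyses drop the imputation or vary the treatment of days under 1000 steps; none departs from missing at random.

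**Conclusion.** The concern holds in a limited form. The protocol permits removal from the study for poor adherence, without a criterion and in an unblinded setting, and week-12 MVPA is then lost. This can make the missingness depend on activity during the intervention. It undermines intention-to-treat under missing at random, mainly for the primary ANOVA with multiple imputation.

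The size cannot be known from the documents. It runs from about 0 with equal removal to about 2.5 to 5 min/day under 5% v 25%, or half to one standard error of a main effect (2.5/5 to 5/5), against the 15-minute effectiveness threshold. These figures assume a 20-minute SD, removal of the least active, a correlation of 0.4 to 0.8 and a complete-case comparison. Imputation using baseline MVPA would reduce them somewhat. This should be changed because the repair is cheap; the documents do not show that bias will occur.

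**What to change.** - Reconcile sections 4.6 and 4.6.1 with section 6.5.4, and correct the clause that lists adherence itself as a ground so that the sponsor's intention is clear.
- Whatever rule the sponsor keeps for ending the intervention, state separately when follow-up ends. Fitbit data through week 12 and Visit 5 would still be requested unless the participant withdraws consent. Section 4.6.1 then needs to say how return of the tracker at an early termination visit fits with this.
- Define the primary analysis set as all randomised participants, analysed as assigned, and say what evaluable means in section 6.6.
- Add observed post-baseline MVPA and wear adherence to the imputation predictors.
- Record the reason for each discontinuation and tabulate it by factor level. A delta-adjusted sensitivity analysis would cover departures from missing at random.

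The cost is protocol and analysis-plan wording plus some staff effort to follow less engaged participants. The tracker and Visit 5 are already in the protocol. Participants who do not wear the device will still have no week-12 data, so the change reduces the problem without removing it.
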